## **8 STATISTICAL CONSIDERATIONS**

The primary goal of this trial will be to assess time to progression, defined as progressive disease, toxicity at a level of severity that precludes the patient continuing on the protocol, or death. Patients will be accrued up to a maximum sample size of 50. Safety monitoring of failure time will be done as follows. Every 2 months, the data from each patient will consist of the time to failure. We define  $T_i$  to be the Time to Progression for the  $i$  th patient

parameterized via a median parameter such that  $T_i | Q_E \sim \text{Exp}(Q_E)$  and  $\text{Median}(T_i) = Q_E$ . We assume that  $Q_E$  has prior distribution  $\text{Inverse Gamma}(a_E, b_E)$  with expectation  $b_E / (a_E - 1)$ . Thus, for each treatment the posterior distribution of  $Q_E | \text{Data}$  is

$\text{Inverse Gamma}(a_E + m_E, b_E + \ln(2) \sum T_i)$  (where  $m_E$  is the number of events in the trial). *A*

*priori*, it is assumed that the median PFS time  $Q_E$  follows an inverse gamma distribution with shape parameter= 2 and scale parameter =17.6761. This prior distribution has median of 10.5 months. The historical median PFS time is represented by  $Q_S$ . In addition,  $Q_S$  is assumed to follow an inverse gamma distribution with shape parameter= 2000 and scale parameter =21000. (This prior also has median of 10.5 months).

The trial will be stopped early if, based on the current data,  $\Pr(Q_E > Q_S + 3.5 | \text{data}) < 0.065$ . That is, the trial will be stopped early if, it is very unlikely that the median time to progression with the experimental therapy (temozolomide and lapatinib) is less than the historical median time to progression for the standard treatment as described in the literature. The rule will be applied every 2 months, with the probability criterion recomputed based on the most recent data available at that time. Based on an anticipated accrual rate of 2.5 patients per month, the trial is expected to complete accrual in 40 months.

To obtain operating characteristics of the early stopping rule, the trial was simulated under three scenarios, which we have summarized in the Table below. The design's operating characteristics are as follows. Each entry in the table is the mean from 2000 simulated trials:

**Table Operating Characteristics.** Maximum sample size 50

Case	Median Time to Progression	Pr(Stop Early)	# Patients (25%,75%)
Scenario 1	2.0	1	16.435 ( 13, 19 )
Scenario 2	7.0	0.896	36.694 ( 27, 50 )

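### Section 8: the early-stopping formula, its explanation in words and its operating-characteristics table do not describe the same rule; as written, the formula stops 19–27% of trials of a 14-month regimen, not 3.4%

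*Combined protocol and SAP*

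**What the plan says.** Section 8 contains every input to the rule.

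- **Prior for the experimental median, Q_E:** inverse gamma with "shape parameter= 2 and scale parameter =17.6761".
- **Historical median, Q_S:** inverse gamma with "shape parameter= 2000 and scale parameter =21000".
- **Update:** exponential failure times. The posterior for Q_E is inverse gamma with shape a_E + m_E and scale b_E + ln(2) × ΣT, where m_E "is the number of events in the trial".
- **Formula:** stop early if Pr(Q_E > Q_S + 3.5 | data) < 0.065.
- **Explanation in words:** introduced as a restatement of the formula, it says the trial stops if "it is very unlikely that the median time to progression with the experimental therapy (temozolomide and lapatinib) is less than the historical median" time for standard treatment.
- **Looks:** "The rule will be applied every 2 months, with the probability criterion recomputed based on the most recent data available at that time". No minimum number of patients before the first look is given, and nothing is said about looks after accrual ends.
- **Size:** "Patients will be accrued up to a maximum sample size of 50". Accrual is put at 2.5 patients per month and also at 40 months in total.
- **Table:** Pr(stop early) is 1, 0.896, 0.173 and 0.034 at true medians of 2, 7, 10.5 and 14 months. Mean enrolment is 16.4, 36.7, 47.4 and 49.1. "Each entry in the table is the mean from 2000 simulated trials".

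**The concern.** The formula and the sentence that explains it disagree on their face. The formula is a futility rule with a 3.5-month margin. The sentence has no margin and, read literally, stops the trial when the regimen looks better than historical.

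The table also looks wrong for the formula. A rule that demands evidence of a 3.5-month gain should often stop a regimen that is only equal to historical, yet the table shows this in 17.3% of trials.

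This is the only rule in Section 8 for stopping the trial, and the table is its only stated justification. If the table belongs to another rule, the plan's stated risk of abandoning a regimen that reaches 14 months (10.5 + 3.5) is not the risk the trial ran.

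**Working it through.** **1. Priors.** The median of IG(2, 17.6761) is 10.53 months and that of IG(2000, 21000) is 10.50. Both agree with the 10.5 that Section 8 states, so the parameterisation is read correctly.

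**2. What the margin does before any data.** Q_S is almost fixed at 10.5, so the formula compares Q_E with about 14. For shape 2, Pr(Q_E > c) = 1 − e^(−x)(1 + x), with x = 17.6761/c.

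- c = 10.5: x = 1.683, probability 0.50.
- c = 14: x = 1.263, probability 0.36.

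The formula therefore starts nearer its cut-off than a rule without the margin.

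**3. What the margin does to the boundary.** With 10 events the posterior is IG(12, 17.6761 + 0.6931 × S), where S is total follow-up in months.

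- With the margin, the probability reaches 0.065 at S = 120.7: (17.6761 + 83.66)/14 = 7.24. The raw median estimate is then 0.6931 × 120.7/10 = 8.4 months.
- Without it, S = 84.1: (17.6761 + 58.29)/10.5 = 7.24. The raw estimate is 5.8 months.

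These are materially different rules.

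**4. Accrual rate.** At 2.5 per month, 50 patients take 50/2.5 = 20 months. Forty months implies 50/40 = 1.25 per month. Both rates were run.

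**5. Simulation.** 20,000 trials per cell, exponential times, Poisson entry, the posterior as printed, looks every 2 months, maximum 50. Looks were taken either during accrual only or for 8 more months. The 8 months is an assumption, borrowed from the separate credible-interval simulation in Section 8.

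| Rule | Accrual per month | Looks | Median 7 | Median 10.5 | Median 14 |
|---|---|---|---|---|---|
| Table in Section 8 | – | – | 0.896 | 0.173 | 0.034 |
| Formula as written | 2.5 | accrual only | 0.972 | 0.560 | 0.197 |
| Formula as written | 2.5 | + 8 months | 0.998 | 0.705 | 0.232 |
| Formula as written | 1.25 | accrual only | 0.997 | 0.708 | 0.249 |
| Formula as written | 1.25 | + 8 months | 0.999 | 0.777 | 0.267 |
| Margin removed | 2.5 | accrual only | 0.736 | 0.145 | 0.027 |
| Margin removed | 2.5 | + 8 months | 0.886 | 0.178 | 0.029 |

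Independent runs with other random seeds gave 0.185–0.269 at 14 months for the formula as written. With 2000 trials, the standard error of the tabulated 0.034 is √(0.034 × 0.966/2000) ≈ 0.004, so simulation error cannot explain the gap.

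**6. Can an unstated detail rescue the formula?** Requiring 10 to 30 patients before the first look still leaves 0.13–0.23 at 14 months. No accrual rate from 0.5 to 20 per month reproduces all rows with the margin in place.

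**7. Patient numbers.** With the margin removed, 2.5 per month, 8 months of further looks, and patients counted one 2-month interval after the stopping look, mean enrolment (quartiles) is 16.3 (13, 19), 37.5 (27, 50), 47.4 (50, 50) and 49.4 (50, 50). The table prints 16.4 (13, 19), 36.7 (27, 50), 47.4 (50, 50) and 49.1 (50, 50). The formula as written gives a mean of about 23–28 at a true median of 7 at 2.5 per month, and about 16 at 1.25 per month.

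**8. The sentence taken literally.** Stopping when Pr(Q_E < Q_S | data) < 0.065 stops no trials at a true median of 2, about 1% at 7, 15–23% at 10.5 and 50–74% at 14, across the same accrual rates and look schedules. That matches neither the formula nor the table.

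**The case against.** The strongest reply has four parts.

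- **Only two rules.** The word less in the explanation is probably a slip for greater. Corrected, the sentence becomes the zero-margin futility rule that fits the table, and the formula is the odd one out. This is a fair reading. It does not help the formula, which is the operative text.
- **The cause is not proved.** Keeping the margin but omitting ln(2) from the posterior update, with 28 months of looks after accrual, gives 1.00, 0.88, 0.16 and 0.035, also close to the table. Its patient quartiles fit less well, (12, 18) and (25, 50) against (13, 19) and (27, 50), and neither the omission nor the long follow-up is in the plan. A coding error in the original simulation therefore remains possible, and this stands as a limit on diagnosis. Under either explanation the table is not that of the printed rule.
- **Removing the margin is not enough.** The match also needs 2.5 per month and looks after accrual. At 1.25 per month with 8 months of further looks, the zero-margin rule gives about 0.92–0.93, 0.21 and 0.03, with smaller enrolment than printed. This stands and is carried into the fix.
- **Accrual is closed** (Section 2.3), so little harm can now occur prospectively. True, but the reported operating characteristics are still wrong, and the rule applied at each look still has to be documented.

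**Conclusion.** The concern holds. Read literally, the formula, the explanation and the table are three different rules. If the explanation is treated as a slip in direction, two remain and the formula conflicts with the table.

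At a true median of 14 months the printed formula stops 19–27% of trials against a stated 3.4%, which is 0.19/0.034 = 5.6 to 0.27/0.034 = 7.9 times as often. At 10.5 months it stops 56–78% against 17.3%.

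The ranges cover both implied accrual rates and looks with or without 8 months after accrual, under the plan's own exponential model. Which of the three texts was intended cannot be settled from the document.

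**What to change.** Decide which rule was intended and make all three texts state it.

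- **If the tabulated properties are intended:** delete the 3.5-month margin from the formula, and confirm the table under the accrual rate and look schedule actually specified.
- **If the margin is intended:** keep it and replace the table with re-simulated values. If a low false-stopping risk at 14 months is wanted, recalibrate the cut-off. At 2.5 per month, a cut-off near 0.01 gives about 0.03–0.04 at 14 months and 0.20–0.33 at 10.5. At 1.25 per month the corresponding figures are about 0.04–0.05 and 0.32–0.41, so the choice depends on the accrual rate.
- **In both cases:** reword the explanation so that the trial stops when it is very unlikely that the experimental median exceeds the historical one (by 3.5 months, if the margin stays).
- **State alongside the table:** one accrual rate (2.5 per month and 40 months cannot both hold for 50 patients), any minimum enrolment before the first look, whether looks continue after accrual, and when patients are counted. Check the ln(2) term in the simulation code. The text announces three scenarios but the table lists four.
- **Because accrual is closed:** record which rule was applied at each look, and report the operating characteristics of that rule.

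The cost is one short simulation and the correction of a formula, a sentence and a table. No patients or procedures are affected.

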- In addition, any subject who develops clinical signs and symptoms of cardiac failure should undergo an LVEF assessment and ECG.

3.7.8 After enrollment on the clinical trial, patients will complete as baseline measures the MDASI-BT or MDASI-SP. The patient will continue to complete the MDASI-BT and/or MDASI-SP at the time of clinical evaluation with MRI as long as the clinical therapy is being administered, unless clinical deterioration makes self-report not possible before that time. The time when patients are unable to complete the self report questionnaires will be used as part of the study analysis. The MDASI-BT and/or MDASI-SP will be completed only by the patient, unless changes in vision or weakness make this difficult. If this occurs, then the caregiver or research assistant may read the questions to the patient or assist with marking the severity number or score as described by the patient. A patient caregiver may complete the questionnaires as a patient-preference proxy if the patient’s deficits preclude self report.

3.7.9 Off treatment follow-up will continue on the following schedule until the patient meets off study criteria.

3.7.9.1 For patients with stable disease or response, MRI surveillance should continue every 2 months for 1 year after treatment completion, then every 3 months for 1 year, then every 4 months for 1 year, then every 6 months until progressive disease is noted, death or lost to follow-up.

3.7.9.2 Patients removed from study treatment for disease progression or treatment-related toxicity should continue to be followed with quarterly (every 3 month) updates of treatment regimens, disease status and survival.

3.7.9.3 Stable disease (SD) patients who develops progression while being followed on the “off treatment follow-up schedule”, will continue with follow-up requirements on the PD off treatment follow-up schedule, until patient meets off study criteria.

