Scenario 3	10.5	0.173	47.354 ( 50, 50 )
Scenario 4	14.0	0.034	49.054 ( 50, 50 )

We also summarize the median lower and median upper credible intervals for this trial on an assumption of that the data follows an exponential distribution (with median survivals summarized in the Table below). To calculate the expected lower and expected upper credible intervals we simulated progression free survival data (1000 simulations) from exponentially distributed data and assuming observations without events were censored at 48 months (40 months of accrual and 8 months of additional follow-up). For each simulation we recorded the lower (1st decile) and upper (9th decile) credible sets from the posterior distribution of the median PFS parameter. At the end of the simulation we then calculated and recorded below the median 1st decile and median 9th deciles from the vector of recorded deciles obtained from our simulation.

True Median Survival	Median 1 st decile and Median 9 th decile	Credible Limits
10.5 Months		(8.72, 12.50)
14 Months		(11.52, 16.66)

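### Section 8: 50 patients at 2.5 per month take 20 months, not 40, and the credible limits give every patient 48 months of follow-up, which overstates planned precision

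*Combined protocol and SAP*

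**What the plan says.** All the design figures are in section 8, Statistical Considerations.

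- Size: "Patients will be accrued up to a maximum sample size of 50".
- Accrual: "Based on an anticipated accrual rate of 2.5 patients per month, the trial is expected to complete accrual in 40 months".
- Precision of the primary endpoint: "we simulated progression free survival data (1000 simulations) from exponentially distributed data", "assuming observations without events were censored at 48 months (40 months of accrual and 8 months of additional follow-up"). For each simulated trial the authors "recorded the lower (1 st decile) and upper (9 th decile) credible sets from the posterior distribution" of the median PFS parameter, and then took medians over the simulations. The result is an 80% interval of (8.72, 12.50) for a true median of 10.5 months and (11.52, 16.66) for 14 months.
- Model: exponential times, with an inverse gamma prior on the median with "shape parameter= 2 and scale parameter =17.6761". The update adds m to the shape, where m "is the number of events in the trial", and adds ln 2 times the summed observed times to the scale.

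Section 3.7.9.1 keeps patients who have not progressed under MRI surveillance after treatment, finally at the widest interval, "then every 6 months until progressive disease is noted, death or lost to follow-up".

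**The concern.** There are two separate problems. First, the sample size, the monthly rate and the accrual duration cannot all be true, and section 8 mentions no ramp-up or screen failure that would reconcile them. The doubtful figure is also not isolated, because it is carried into the 48-month follow-up used for the precision table.

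Second, 48 months is the length of the whole study, from first entry to analysis. It is not the follow-up of a typical patient. If every patient is given the full calendar length, the simulation counts events that would not yet have been seen.

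The table is the plan's only statement of how precisely median PFS will be estimated. It also shows how far the design separates 10.5 from 14 months, the 3.5-month difference used in the stopping criterion.

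**Working it through.** **Accrual.** Duration = N / rate = 50 / 2.5 = 20 months. Forty months would need 50/40 = 1.25 patients per month, or 40 × 2.5 = 100 patients.

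**Follow-up on the 40 + 8 calendar.** Individual follow-up runs from 48 months (first patient) to 8 months (last patient). With uniform entry the mean is (48 + 8)/2 = 28 months.

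**Expected events, M = true median, N = 50.**

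- Common censoring at 48: 50 × (1 − 2^(−48/M)). M = 10.5: 50 × (1 − 0.042) = 47.9. M = 14: 50 × (1 − 0.093) = 45.4.
- Uniform entry, follow-up from 8 to 48 months: 50 × {1 − [M/(40 ln 2)] × [2^(−8/M) − 2^(−48/M)]}. M = 10.5: 50 × (1 − 0.379 × 0.548) = 39.6. M = 14: 50 × (1 − 0.505 × 0.580) = 35.4.

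**Credible limits.** For each simulated trial of 50 exponential times, the posterior is Inverse Gamma(2 + m, 17.6761 + ln 2 × ΣT). The 10th and 90th percentiles are recorded and their medians taken over 1,000 trials, as the plan describes. The whole exercise was repeated 400 times, so the Monte Carlo error of a 1,000-trial table is known. The table gives averages over the repeats; the last column compares each width with the printed 3.78 and 5.14.

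| Follow-up scheme | True median 10.5: limits (width) | True median 14: limits (width) | Width vs printed |
|---|---|---|---|
| Printed in the plan | (8.72, 12.50) (3.78) | (11.52, 16.66) (5.14) | – |
| Everyone censored at 48 | (8.76, 12.60) (3.84) | (11.54, 16.76) (5.22) | +2%, +2% |
| Staggered, 40 + 8 | (8.63, 12.85) (4.23) | (11.27, 17.17) (5.90) | +12%, +15% |
| Staggered, 20 + 8 | (8.51, 13.10) (4.59) | (11.03, 17.56) (6.54) | +21%, +27% |
| 20 months' accrual, analysis at 48 | (8.73, 12.67) (3.94) | (11.46, 16.87) (5.42) | +4%, +5% |

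**Which scheme produced the printed figures.** Under common 48-month censoring each printed limit is within 1% of the reproduction. The printed widths are somewhat low, by 2.5 and 2.1 Monte Carlo standard deviations. Under staggered 40 + 8 entry they are 13 and 15 standard deviations too low; under 20 + 8, 19 and 21; under 20 months of accrual analysed at month 48, 5 and 6. A common 60-month censoring time would fit slightly better still (widths 3.80 and 5.10), but nothing in section 8 suggests 60 months, and it too gives everyone the same long follow-up.

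**Like for like.** Against the reproduced 48-month widths, staggering on 40 + 8 costs 4.225/3.843 = 1.10 and 5.902/5.222 = 1.13. As a rough check, width varies as 1/√(m + 2): √(49.9/41.6) = 1.10 and √(47.4/37.4) = 1.13.

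**Separation of the two medians.** The overlap of the two intervals is 12.50 − 11.52 = 0.98 months as printed, and 12.85 − 11.27 = 1.58, about 1.6 months, on 40 + 8.

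**The case against.** The accrual contradiction cannot be defended. The case against the precision point has five parts.

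1. *The 12% and 15% mix two effects.* They are measured against printed widths that are slightly narrower than the plan's own method gives. This stands: staggering alone costs 10% and 13%.
2. *The size depends on a calendar already shown to be unreliable.* This also stands. If 2.5 per month is right and the analysis stays at month 48, the loss is 4% to 5% against print; with 20 + 8 it is 21% to 27%. The 12% and 15% belong to the calendar the plan states.
3. *The 48-month censoring is openly stated.* True, but the bracketed justification builds it from accrual plus additional follow-up, which describes study length and not follow-up per patient.
4. *Nothing depends on it.* The stopping rule uses a posterior probability and not these limits, the final posterior will use actual follow-up, accrual is closed (section 2.3), and MRI surveillance runs to progression. All true. If the last patient is assumed to have at least 24 months, widths are 3.90 and 5.33 (40-month accrual) or 3.99 and 5.53 (20-month), only 3% to 8% above print. But section 8 names no analysis time other than the 48 months.
5. *The recomputed limits assume all 50 patients enter*, while the plan's own table gives early-stopping probabilities of 0.173 and 0.034 at these medians. This is correct. The simulation described in section 8 does not mention early stopping either, so the comparison is fair, but the assumption should be stated.

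**Conclusion.** The concern holds on both counts. The 40-month accrual figure does not follow from 50 patients at 2.5 per month, and the documents do not show which of the three figures is wrong. Independently of that, the printed credible limits rest on the same long follow-up for every patient, which the stated 40 + 8 calendar cannot deliver. On that calendar the intervals should be 12% and 15% wider than printed, and the table in effect counts about 8 and 10 events too many (47.9 against 39.6; 45.4 against 35.4).

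These sizes assume exponential times, uniform entry, full enrolment of 50 and no dropout. The consequence is limited to the documented planning precision: no boundary, treatment decision or final estimate uses these limits. It should be corrected, because a report quoting the table would claim a planned precision that the stated schedule did not support.

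**What to change.** - State one consistent set of sample size, accrual rate, accrual duration and analysis time. For 50 patients that could be 2.5 per month over 20 months, or 1.25 per month over 40 months.
- Rerun the credible limits with each patient censored at analysis time minus own entry time, and replace the table with the matching result from the working above: staggered 40 + 8, staggered 20 + 8, or 20 months of accrual analysed at month 48.
- Say whether the limits assume full enrolment or allow for early stopping.
- State which accrual rate the operating-characteristics table used. The rate sets how many patients enter between the two-monthly looks, and the text does not tie that table to either rate.

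The cost is a rerun of an existing simulation and a few restated figures. The stated precision becomes somewhat less favourable. With accrual closed, enrolment is unaffected.

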### Secondary Efficacy Analysis

The secondary endpoint of this trial is anti-tumor activity as determined by the overall response (CR or PR) rate. MacDonald criteria will be used to determine the overall response. Patients must have completed at least 4 weeks of treatment to be considered evaluable for overall response, unless treatment is stopped for neurologic progression. Patients with neurologic progression will be scored as non-responders regardless of duration of treatment.

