#### **1.1.2 Secondary Objectives**

- 1.1.2.1** To determine the efficacy of the combination of lapatinib and temozolomide as measured by objective response in patients with measurable disease.
- 1.1.2.2** To determine the adverse event profile and tolerability of the combination of lapatinib and temozolomide in patients with recurrent ependymoma
- 1.1.2.3** To correlate response, either by objective response or progression-free survival at 12 months with EGFR expression, PTEN expression and MGMT gene promoter methylation status.
- 1.1.2.4** Determine the efficacy of the combination of lapatinib and temozolomide in spinal cord ependymoma as a component of a pilot study.

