### 3.3.1.2 Summary of dose modifications

Dermatologic		
Rash – acne/acneiform 

• Intolerable Grade 2 & Grades 3-4

		
Hold dose.
 

• Re-evaluate at least weekly until AE resolved to <math>\leq</math> 1 or tolerable Grade 2.

• Re-treat at a one dose level reduction

• If AE persists <math>></math> 4 weeks, remove patient from study

 
Patients with Grade 4 AEs related to agent should be taken off study.
 
Note: Grade 2 lapatinib related rash may not automatically require dose reduction. However, for Grade <math>\geq</math> 3 rash or recurrent intolerable Grade 2 rash, reduce 1 dose level.

Gastrointestinal		
Diarrhea 

• Grade 1

• Grade 2

• Grade 3, 4 or intolerable Grade 2:

		
No intervention required
 
Loperamide (4 mg at first onset, followed by 2 mg every 2–4 hrs until diarrhea free for 12 hrs)
 

• Hold dose.

• Loperamide, hold agent until recovery to <math>\leq</math> Grade 1 and then reduce 1 dose level

• If AE persists <math>></math> 4 weeks, remove patient from study

• Patients with Grade 4 AEs related to agent may be taken off study at investigator's discretion.

Ocular/Visual		
Keratitis 

• Grade 1

		

• Preservative-free artificial tears, ointments, and/or other therapies as clinically indicated, with a follow-up examination within 2 weeks.

• Dose reduction not required.

• Grade 2 or 3

		

• Manage as for Grade 1 keratitis.

• Grade 2 persistent (>14 days) or Grade 3: Hold dose. Re-treat at a reduced dose after resolution or amelioration of AE to <math>\leq</math> Grade 1 at the discretion of the investigator.

• Persistent Grades 2 or 3: Remove patient from study for persistent Grade <math>\geq 2</math> keratitis after dose held for 14 days. Ophthalmologic F/U should be scheduled at a frequency determined by the ophthalmologist

Pulmonary/Upper Respiratory		

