## **3.8 CRITERIA FOR REMOVAL FROM PROTOCOL THERAPY AND OFF STUDY CRITERIA**

### **3.8.1 Criteria for Removal from Protocol Therapy**

A genuine effort must be made to determine the reason(s) why a patient fails to return for the necessary visits or is discontinued from the trial. Information regarding the reason for not completing the trial will be recorded on the appropriate case report forms.

It will be documented whether or not each patient completed the clinical study. If for any patient study treatment or observations were discontinued the reason will be recorded on the appropriate case report form. Reasons that a patient may discontinue participation in a clinical study are listed below:

Any patient who receives at least one dose of trial medication will be included in the safety analysis.

- 3.8.1.1** Evidence of recurrent or progressive disease
- 3.8.1.2** Second malignancy
- 3.8.1.3** Development of unacceptable toxicity during treatment
- 3.8.1.4** Non-adherence to the protocol
- 3.8.1.5** Refusal of therapy
- 3.8.1.6** Pregnancy
- 3.8.1.7** At 2 years of protocol therapy

**3.8.2** Off Study Criteria

- 3.8.2.1** Death
- 3.8.2.2** Lost to follow-up
- 3.8.2.3** Withdrawal of consent for continued follow-up
- 3.8.2.4** Protocol defined follow-up completed
- 3.8.2.5** Withdrawal of consent

**3.8.3** Off study procedure

*For participating CERN sites:*

When a subject is taken off-study, notify CCR study coordinator via encrypted email.  
([name] email: [[contact]](mailto:[contact]) )

**3.8.4** POST PROTOCOL THERAPY AND FOLLOW UP

**3.8.4.1** Post Protocol Single Agent Lapatinib

Patients that are showing sustained Complete Response (CR), Partial Response (PR) or Stable Disease (SD) may continue Post protocol single agent therapy with lapatinib. Post protocol lapatinib supply may be obtained through Glaxo Smith-Kline (GSK), using the same drug ordering mechanism as detailed in section 10.2.12 (Agent Ordering/Requests).

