## **4 CONCOMITANT MEDICATIONS/MEASURES**

### **4.1 SUPPORTIVE CARE**

All supportive therapy for optimal medical care will be given during the study period at the discretion of the attending physician(s) within the parameters of the protocol and documented on each site's source documents as concomitant medication.

**4.1.1 Anticonvulsants:** Antiepileptic medications should be used as indicated. However, only patients taking non-hepatic enzyme inducing antiepileptic drugs (non-EIAEDs) or no antiepileptic drugs are eligible to enroll on this trial. Patients must not be taking EIAEDs for at least 2 weeks prior to registration. See Appendix 12.2 for a list of EIAEDs and non-EIAEDs.

During therapy, patients who were previously on a non-EIAED and need to change anticonvulsants should be started on another non-EIAED if at all possible. No delays in treatment would be required.

If patients who were previously on no anticonvulsants require initiation of an anticonvulsant, a non-EIAED should be used if at all possible.

If a patient is started on an EIAED while on the study, he/she should immediately be started on another non-EIAED and the EIAED should be tapered and discontinued as quickly as possible. The patient may continue the lapatinib. The dates that the patient took an EIAED should be noted.

Patients who need to permanently change anticonvulsants but who cannot change to another non-EIAED will be taken off study.

- 4.1.2 Analgesics: As needed.
- 4.1.3 Hematopoietic Growth factors: Permitted for grade 4 neutropenia or neutropenia with fever and should follow American Society of Clinical Oncology guidelines for their use. [\*] Prophylactic use of growth factors is not allowed, nor can they be used to improve blood counts to allow initiation of treatment.
- 4.1.4 Treatment of rash: The acneiform rash associated with lapatinib treatment appears to be treatable with standard acne therapies, including topical and oral antibiotics used to treat acne. Anecdotal reports of improvement have occurred with any of the following: minocycline topical tetracycline, topical clindamycin, topical silver sulfadiazine, diphenhydramine, and oral prednisone (short course). Minocycline recommended dose: 200 mg po bid (loading dose), followed by 100 mg po bid for 7-10 days.
- 4.1.5 Nutritional Supplementation: Permitted.
- 4.1.6 Antacids: Permitted.

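### The 4-week evaluability rule removes patients who stop early from the response denominator, and no all-treated rate is planned; the likely effect is small

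*Combined protocol and SAP*

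**What the plan says.** The Secondary Efficacy Analysis in Section 8 defines the secondary endpoint as the CR-or-PR rate and sets one condition for entering it: "Patients must have completed at least 4 weeks of treatment to be considered evaluable for overall response, unless treatment is stopped for neurologic progression". It then adds: "Patients with neurologic progression will be scored as non-responders regardless of duration of treatment". Objective 1.1.2.1 limits the endpoint to a population, "as measured by objective response in patients with measurable disease", but says nothing about length of treatment.

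The protocol foresees other early stops. Section 3.8.1 lists "Development of unacceptable toxicity during treatment" and "Refusal of therapy". For rash, 3.3.1.2 says "Patients with Grade 4 AEs related to agent should be taken off study". Section 4.1.1 says "Patients who need to permanently change anticonvulsants but who cannot change to another non-EIAED will be taken off study". None of these falls under the exception for neurologic progression.

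The primary endpoint in Section 8 counts as failure "toxicity at a level of severity that precludes the patient continuing on the protocol". The safety analysis takes in every patient from the first dose. For response, no passage plans a rate over all treated patients.

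**The concern.** Whether a patient is dropped depends on what happens after treatment starts. A patient who stops in week 2 because of toxicity is a failure in the primary endpoint, is counted for safety, and is absent from the response rate. All else equal, more early toxicity stops mean a smaller denominator and a higher reported rate. The plan does not ask for the number excluded or the reasons, so a reader could not undo the selection.

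Section 1.2.2 names a 20% response rate among its benchmark data for later trials, so this trial's rate is likely to be read against that figure.

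The exception is also loosely worded. Section 8 does not define neurologic progression. Read literally, an early stop for progression on imaging alone, or an early death, could be dropped as well.

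**Working it through.** The plan gives no target response rate, no power for response and no expected share of exclusions, so there is no figure of its own to reproduce. The check is the direction and size of the effect.

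**Direction.** Section 3.7.3 schedules MRI before cycles 3, 5, 7 and so on. Cycles last 28 days, so the first on-study scan falls at about 2 × 28 = 56 days, or 8 weeks. A patient who stops before week 4 has no scheduled scan before stopping on which a response could be documented. A later one is improbable but possible: after a cardiac stop, planned assessments continue (3.3.1.4.1.4), and off-treatment imaging or follow-up is foreseen (3.6, 3.7.9).

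**Bound.** Take N patients with measurable disease, R responders, X = fN excluded, and r responders among the excluded.

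- Full rate: R/N
- Rate under the 4-week rule: (R − r)/(N − X)
- Ratio of the two: [(R − r)/R] × 1/(1 − f), which is at most 1/(1 − f), with equality only when r = 0

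Enumerating all integer cases for N = 5 to 50 found none above the bound.

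**Inputs for the illustration.** The base rate of 20% is the benchmark in 1.2.2. N = 50 is the maximum sample size in Section 8, assuming that all have measurable disease. N = 35 is an assumption for a smaller measurable group, since 2.1.1.11 does not require residual disease after resection. The excluded counts are assumptions.

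| N | R | X | f | Rate with r = 0 | Factor |
|---|---|---|---|---|---|
| 35 | 7 | 0 | 0 | 7/35 = 20.0% | 1 |
| 35 | 7 | 1 | 2.9% | 7/34 = 20.6% | 1.029 |
| 35 | 7 | 3 | 8.6% | 7/32 = 21.9% | 1.094 |
| 35 | 7 | 6 | 17.1% | 7/29 = 24.1% | 1.207 |
| 50 | 10 | 0 | 0 | 10/50 = 20.0% | 1 |
| 50 | 10 | 1 | 2.0% | 10/49 = 20.4% | 1.020 |
| 50 | 10 | 3 | 6.0% | 10/47 = 21.3% | 1.064 |
| 50 | 10 | 6 | 12.0% | 10/44 = 22.7% | 1.136 |

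With 1 to 3 excluded, the rise runs from 20.4 − 20.0 = 0.4 to 21.9 − 20.0 = 1.9 points. For 20% to become 25%, f = 1 − 0.20/0.25 = 0.20, that is 7 of 35 or 10 of 50.

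**If one excluded patient later responds (N = 35).** With 3 excluded, 6/32 = 18.8%; with 5, 6/30 = 20.0%; with 6, 6/29 = 20.7%. The rise shrinks or reverses.

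**Scale against sampling error.** Exact 95% intervals are 8.4–36.9% for 7/35 and 10.0–33.7% for 10/50. Every shift in the table lies well inside them.

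**The case against.** The case for leaving the rule alone has real weight.

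- **Small f.** Most toxicity rules hold or delay before removal. For lapatinib, rash, diarrhea and other non-hematologic events generally lead to a hold, with removal if the event lasts more than 4 weeks (3.3.1.2). Temozolomide is delayed for up to 4 weeks before it is stopped, and its dose is judged on the preceding cycle (3.3.2). Immediate stops exist, for example for grade 4 rash, confirmed and possibly related pneumonitis, combined ALT and bilirubin elevation, and cardiac events, but they are narrow. Section 10.2.18 reports no grade 3 toxicity on once-daily lapatinib in a phase 1 study, though as a single agent in other tumours. This stands, with the proviso that Section 8 does not say whether held days count as treatment.
- **The benchmark.** A reader might infer that the rule tilts the comparison with the 20% in 1.2.2 in the trial's favour. The documents do not support that. The benchmark series had 28 patients, and 0.20 × 28 = 5.6; 5/28 = 17.9% and 6/28 = 21.4%, and neither rounds to 20%. The benchmark's denominator is unknown, and an evaluable-type rate may even be the closer match.
- **Early death.** A reader might infer that early deaths vanish from the analysis. Section 6.2.3.4 already treats a patient who does not return because of death or decline as progressed, unless the cause is clearly unrelated to the cancer. What remains is a missing cross-reference.
- **A legitimate choice.** A minimum-exposure set for an activity endpoint is defensible and was set in advance. That argues against replacing the planned rate, but not against showing a second one.

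That the shifts lie within sampling error is a weaker reply. The shift is systematic when no excluded patient responds, and an interval computed on the reduced denominator does not account for it.

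**Conclusion.** The point holds and is minor. As written, the rule removes early stops for toxicity, refusal or other non-neurologic reasons from the response rate, and no all-treated rate restores them. Taken alone, this raises the rate by at most 1/(1−f). The bound is reached only if none of the excluded patients responds, which the scan schedule makes likely but not certain. The value of f is unknown, and the 0.4 to 1.9 point range rests on an assumed 20% rate and assumed exclusions of 1 to 3 among 35 to 50 patients.

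A reader might go further and infer that the rule hides toxicity or could change the trial's conclusion. Neither follows. Treatment-limiting toxicity is a failure in the primary endpoint and is tabulated for safety, and response has no decision rule in Section 8. What is affected is how the reported response rate is read.

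**What to change.** Keep the planned 4-week rate and add to the Secondary Efficacy Analysis:

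> The response rate is also reported, with equal prominence, in all patients with measurable disease at baseline (6.2.2.1) who received at least one dose. In this set every patient without a documented CR or PR is a non-responder, including early stops for toxicity, refusal or other cause, death, no post-baseline assessment, and status Unknown (6.2.3.5). The number excluded from the 4-week rate and the reasons are listed.

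Reword the sentence on neurologic progression, which read alone would also cover a documented responder who progresses later:

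> Patients whose treatment stops for progression, including neurologic progression and death or deterioration under 6.2.3.4, and who have no earlier documented CR or PR count as non-responders, however long they were treated.

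Date the addition as made after accrual closed (2.3). Leave the MDASI comparison of responders and non-responders as it is.

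The cost is three added sentences, one reworded sentence and a dated note. No new data are needed. The added rate may be slightly lower than the planned one.
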